Those randomized to the will receive either 40mg of a non-fluorinated injectable glucocorticoid, methylprednisolone acetate (1cc) combined with 1cc of 1% Lidocaine or 1cc f1% Lidocaine plus 1cc of normal saline. The injection will be performed unilaterally if pain is single sided or bilaterally if the pain is in both sacroiliac joint regions The injection will be ultrasound guided and performed by the PI [name] who is trained in musculoskeletal ultrasound and ligamentous injections as a specialist in physical medicine and rehabilitation. [name] and the participant will both be blinded to the type of injectate used. Study visits 2 and 3 will include the same questionnaires and physical examination and will document any change in the pregnancy status. Study visit 4 will occur 6 weeks post-delivery and will include the same questionnaires and physical examination to determine if any chronic pain remains. Patients will be allowed to utilize acetaminophen as needed and the amount utilized in each intervention arm will be recorded. Total study visit time is expected to be 60 minutes for study visit 1 and 30 minutes for visits 2-4. Standard physical examination maneuvers validated for the assessment Protocol Version 4 – 03-06-2015

of pregnancy related PGP will be performed by the PI [name] and include pelvic pain provocation tests and functional stability testing. It will be noted with each maneuver whether the test was positive or negative. They will include:

a. *Patrick's Faber test*: With the patient in supine, the patient's leg is flexed, abducted and externally rotated so that the heel rests on the opposite kneecap. This test is positive with production of pain in the sacroiliac joint.

b. *Posterior Pelvic Pain Provocation (P4) test*: with the patient supine, the femur is flexed to be perpendicular with the table at 90 degrees and the knee is flexed at 90 degrees. A gentle force is applied to the femur in the direction of the examination table. The test is positive when the patient experiences pain in the gluteal region of that leg.

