3.5.5 Adverse event reporting*

The PI or the study nurse coordinator can be reached by pager or phone and will be on call for study patients 24 hours a day. [name], chief Loyola Maternal Fetal Medicine will also be available for patient adverse reactions. Adverse events to be recorded will include excessive bleeding, infection, significantly worse pain at the 7 day post-injection phone check, fetal distress or demise, fall post injection, and/or maternal hospital admission. If the subject has persistent post injection side effects of flushing, nausea, vomiting or insomnia, this will be reported. If any other unanticipated adverse event occurs, this will also be immediately reported to the IRB. A data safety monitoring plan is detailed below in the section titled “Safety Monitoring Plan.”

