treatment outweighs the minimal risk. Both study groups will receive standard of care physical therapy (cost covered by their insurance), a proven treatment for pregnancy related pelvic girdle pain. For the intervention group that receives methylprednisolone, expected immediate side effects might include vasovagal reaction and delayed (2 days) side effects might include injection site soreness, sweating or facial flushing³⁰. Toxicity at high levels and multiple dosing effects are not expected given that this is a low dose of corticosteroid injected locally. Infection rates associated with injection are low and typically seen in intraarticular not extraarticular injections³¹. A possible rare adverse effect might include allergic reaction. If an adverse reaction or side effect occurs, the subject will be seen by [name] (maternal fetal medicine) at Loyola. This will also be immediately reported to the IRB.

The benefits of the intervention include the possibility of superior pain relief compared with placebo. Lidocaine has been safely and successfully used in pregnant women undergoing amniocentesis.³² Oral steroids are used for other conditions in pregnancy such as asthma, rheumatoid arthritis, and severe sinusitis. They are also utilized in the treatment of pre-term labor to assist in the development of fetal lung maturity. Methylprednisolone is a class B drug and its well-established clinical utility in other diseases lends to the safety of its potential use in this debilitating pain condition (PGP) in pregnancy and warrants further study for the treatment of musculoskeletal pain.

I. Safety Monitoring Plan

a. Definition of adverse events, serious adverse events

- i. An adverse event is defined as any symptom or medical problem experienced by the participant following consent to participate. All adverse events must be reported to the study physician and regulatory coordinator within three working days of discovery. All adverse events that occur during the trial will be recorded on the adverse event log. The investigator study physician will ask patients at each visit "Have you experienced any

symptoms or medical problems since your last visit?” and will subsequently record all events using the adverse event log.

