- ii. Serious adverse events must be reported to the University’s IRB, Principal Investigator, Study Physician, and Regulatory Coordinator within 24 hours of discovery using the Serious Adverse Event Case Record Form. An SAE is defined as any adverse drug experience that results in:

1. Death
2. A life-threatening adverse experience
3. An important medical event
4. Inpatient Hospitalization (or prolonged hospitalization)
5. Persistent or significant disability/incapacity
6. A congenital anomaly or birth defect

- iii. Finally, the principal investigator or her designee will record on the adverse event log: (1) A description of the event, (2) the start date of the event, (3) the stop date of the event, (4) the expected relationship to the study drug, (5) Whether any action was taken with the study drug, and (6) the primary outcome of the event. Additionally, the principal investigator or her designee will record any change in an ongoing adverse event.

b. What procedures will be used to monitor subject safety?

- i. All participants will complete a general physical examination prior to randomization. Data will be recorded using the General Physical Case Record Form.
- ii. Vital signs (weight, height, temperature, seated blood pressure, and seated heart rate) will be taken at each visit. Data will be recorded using the Vitals Case Record Form.

- iii. [Description of labs used to monitor mother and child health, and how often those labs will be collected and evaluated. Also describe whether the participant will receive a copy of their laboratory results, and whether such a report will be given directly to them or sent to their personal healthcare provider].
 - iv. Participants are encouraged to report any (1) New adverse event, (2) whether any existing adverse events have worsened or resolved, (3) whether there are any changes to their concomitant medications, and (4) whether a medication was required to treat an adverse event. Such information is recorded on the adverse event log CRF and concomitant medication log CRF as necessary.
- c. Who (list names) will identify, document, and report adverse events?**
- i. All named research members may receive information about an adverse event and, consequently, are required to report such events as described in this protocol.

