 - ii. The principal investigator and/or study physician will evaluate (1) The expected relationship of the event with the study drug and (2) Whether any action should be taken regarding the study drug following an adverse event.
- d. What is the frequency for review of summarized safety information and who will perform the review (e.g., safety monitoring board)?**
- i. The Principal Investigator or her designee will alert Loyola University Chicago Health Sciences Division IRB#1 *promptly* of all serious and any unexpected adverse events associated with the project (or the study supplement). **Associated** is defined as any adverse experience that is *possibly, probably, or definitely* related to the study drug. **Unexpected** is

defined as any untoward experience following informed consent that is not listed as a risk in the informed consent document.

ii. The Principal Investigator will also *promptly* report non-compliance with the activities described in the protocol, participant complaints, and any billing errors. Additionally, the PI will *promptly* report:

1. Serious adverse events (including events that produce injury or death, an event leading to hospitalization or lead to prolongation of a current hospital stay)
2. The enrollment of a patient on a study that is no longer enrolling participants
3. Any patient reporting a billing problem as a result of project participation
4. Any participant who has voiced a complaints about some aspect of the project or the consent document
5. Any unanticipated, untoward, or unexpected adverse event not covered above including rare adverse events or adverse events that occur at an unexpected rate
6. Protocol deviations
7. Investigational drug/device brochures and revisions

e. What are the stopping rules with regard to efficacy and safety?

- i. A decision to stop the study may be made when there are documented serious maternal or fetal adverse events that can be possibly, probably, or definitely attributed to study drug exposure and are deemed to exceed the potential benefits of the study drug.
- ii. The principal investigator, the Institutional Review Board, or United States Government Regulatory Authorities (e.g., the Federal Drug Administration or

FDA) may stop this study at any time. If this happens, the research team will be in direct contact with the Institutional Review Board and regulatory agency regarding participants' suspension or termination of study drug.

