- iii. The investigator may decide to stop a subject's participation in this trial at any time. This may happen, for example, if the participant fails to comply with the protocol activities or experiences an adverse event. If this happens, the research team will be in direct contact with the Institutional Review Board and will, with the participant's informed consent, continue to follow the participant off study drug for pregnancy outcome and fetal adverse events.

5. Importance of Clinical Research in Pregnant Women

In October 2010, the Office of Research on Women's Health (ORWH) convened a scientific research forum, *Issues in Clinical Research: Enrolling Pregnant Women* in partnership with several National Institutes of Health (NIH) institutes, centers, offices and the Food and Drug Administration (FDA), to address the ethical/ Institutional Review Board (IRB) and recruitment issues that investigators face in the conceptualization, initiation, and conduct of clinical research studies that enroll pregnant women. During this forum, the audience was challenged to address gaps in knowledge about medical treatment and pregnancy, to increase the evidence base on the inclusion of pregnant women in clinical research, and to conduct appropriate scientifically- and ethically-designed clinical research. Medical ethicists, clinical investigators, academic researchers, and those with an interest in and concern about clinical research in women provided information related to risk perception, risk reasoning, and the ethics of balancing risks and benefits in the clinical arena.

The NIH strategic plan for research on women's health identified six major goals for women's health research, one of which was the goal of increasing research to "*actualize personalized prevention, diagnostics and therapeutics for girls and women.*" Among specific

objectives listed for the goal were two objectives that directly addressed pregnancy: 1) *“encourage research on safe and effective interventions for conditions affecting pregnant women”*; and 2) *“expand research on pregnancy related conditions, such as preeclampsia, diabetes, and hypertension on the subsequent health of women and their offspring.”*

The report from this forum (<http://orwh.od.nih.gov/resources/policyreports/pdf/ORWH-EPW-Report-2010.pdf>) made several poignant statements relevant to [name] proposed project.

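### Fetal harm is reportable and can stop the trial, but the text does not require a birth or newborn outcome record for every woman

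*Combined protocol and SAP*

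**What the plan says.** **Fetal events matter to the plan.** Section 3.5.5 lists among the events to record "fetal distress or demise, fall post injection, and/or maternal hospital admission". The serious adverse event categories (Safety Monitoring Plan, a.ii) include "A congenital anomaly or birth defect". The stopping rule (e.i) may be used when there are "documented serious maternal or fetal adverse events that can be possibly, probably, or definitely attributed to study drug exposure".

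**The procedures for finding them are thinner.** Part b of the Safety Monitoring Plan has four items. Items b.i (general examination) and b.ii (vital signs) concern the woman, and b.iv relies on what she reports. Item b.iii alone mentions the child, and it is an instruction to the author: "Description of labs used to monitor mother and child health, and how often those labs will be collected and evaluated".

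**Visits.** Section 3 says: "Study visits 2 and 3 will include the same questionnaires and physical examination and will document any change in the pregnancy status". Those visits fall 4 and 8 weeks after injection. For the postpartum visit it says: "Study visit 4 will occur 6 weeks post-delivery and will include the same questionnaires and physical examination to determine if any chronic pain remains". Appendix I has no row for delivery or birth outcome at any time point.

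**Adverse event enquiry.** Item a.i opens: "An adverse event is defined as any symptom or medical problem experienced by the participant following consent to participate". It then has the study physician ask at every visit about symptoms or medical problems since the previous one, and record the answers.

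**Pregnancy-outcome follow-up.** Item e.iii says that, for a woman whose participation the investigator stops, the team will, with her consent, "continue to follow the participant off study drug for pregnancy outcome and fetal adverse events".

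**The concern.** The trial gives a corticosteroid in the second or third trimester, and its safety plan treats fetal harm as reportable and as a ground for stopping. A rule of that kind works only if the events are looked for in everyone. Here the text names the events without setting a step that finds them for each woman.

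For a woman who completes the trial, a stillbirth, neonatal admission or anomaly after the 8-week visit is recorded if she or a clinician raises it. Section 1.3 allows referral from other hospitals and practices, so the site may not hold her delivery record. Two things are then at stake. The fetal part of the stopping rule would act on incomplete information, and the final report could not give birth outcomes by arm with a denominator. An empty log could not be read as an absence of events.

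**Working it through.** The plan gives no figure of its own to reproduce on this point. The check is mainly a reading of each place where a birth outcome could be collected, followed by two short calculations.

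**1. Part b, item by item.** Three of the four items are complete (b.i, b.ii, b.iv), and none of the three names the fetus or newborn. The fourth, b.iii, is unfilled. Even if filled, it asks about laboratory tests, so completing it would not by itself create a birth record.

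**2. Each contact (section 3, item a.i, Appendix I).**

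- Day 7 telephone call: side effects and adverse events.
- 4 and 8 weeks: questionnaires, examination, change in pregnancy status. A delivery or loss by then would be noted, but no newborn items are named.
- 6 weeks postpartum: questionnaires and examination, with chronic pain as the stated purpose. The general adverse event question applies here too, but it asks what the woman herself has experienced.
- Women who miss the postpartum visit: no step is stated.
- Women stopped by the investigator: follow-up for pregnancy outcome and fetal events, with consent (e.iii).

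Stopped women are thus the only group for whom pregnancy-outcome follow-up is written down.

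**3. How much pregnancy lies beyond the 8-week visit.** Let g be the gestational week at injection and B the week of birth. Weeks remaining = B − (g + 8), or none if this is negative. Section 3.2 excludes women before 13 weeks, so g starts at 13. B is not in the documents; 40 and 37 are assumed.

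- B = 40: g = 13 gives 40 − 21 = 19; g = 20 gives 40 − 28 = 12; g = 28 gives 40 − 36 = 4; g = 32 gives 0.
- B = 37: g = 13 gives 37 − 21 = 16; g = 20 gives 37 − 28 = 9; g = 28 gives 37 − 36 = 1; g = 29 gives 0.

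The uncovered stretch is long for women injected early and nil for those injected late.

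**4. What a complete record could show.** Section 3.5.1 enrols 60 women and Appendix II puts 30 in each group. If every birth in the steroid arm is checked and none has a given event, the exact two-sided 95% upper limit on the risk is 1 − 0.025^(1/30) = 0.1157, or 11.6%. That limit holds only if all 30 births are known. The documents do not say what share of events would reach the log without a scheduled record, so no figure is put on the loss.

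**The case against.** **A post-birth enquiry exists.** The physician asks about medical problems at each visit, and one visit falls 6 weeks after delivery. A woman whose baby was ill may well say so. This stands, and it rules out the stronger reading that nothing is asked after birth or that fetal events cannot enter the record. What remains is that the question concerns the mother and reaches only attenders.

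**Preterm birth is partly covered.** The postpartum visit is timed from delivery, and the due date is collected, so gestational age at birth can be derived for attenders. Deliveries before 8 weeks should appear as a change in pregnancy status, and maternal hospital admission is recordable. A reader might infer from section 3.7, which adds 10% for loss to follow-up and premature delivery, that women who deliver early are the ones who will be missed. That sentence only enlarges the sample and does not support the inference.

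**Item e.iii can be read more broadly.** Its verb may imply that everyone is already followed for pregnancy outcome and that this persists after stopping. The reading is possible, but no other text sets up such follow-up, so it should be stated.

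**Two further stronger readings fail.** Section 3 gives the study duration as 8 weeks per patient, from which one might conclude that later births fall outside the recording window. The scheduled postpartum visit argues against this. One might also cite the absence of newborn items in the personal health information list, but that list covers items collected during pregnancy, so it says little.

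**The forms are unseen.** Section 3.6 refers to Appendix IV for the study forms, and these are not in the text. They may hold birth fields. It therefore cannot be said that no birth data were collected, only that the written plan does not require them.

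**The stopping rule is discretionary and case-based.** It does not compare rates by arm, and 30 women per arm cannot exclude uncommon harm. Both points are correct. Still, an event must be documented before it can be attributed, and recruitment over one year (Appendix I) leaves time for early births to inform later enrolment.

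**Conclusion.** The concern holds as a gap in systematic ascertainment. Fetal events are named, reportable and able to stop the trial, but the text sets no birth or newborn outcome record for every woman. The gap concerns all 60 women, 30 of them assigned to steroid. It is widest for those injected early: up to 19 weeks of pregnancy after the 8-week visit with birth at 40 weeks, or 16 with birth at 37, both assumed. It is narrowed by the adverse event question at the postpartum visit and by the derivable delivery timing for attenders.

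The conclusion rests on the text alone and would weaken if the Appendix IV forms contain birth fields. The unfilled b.iii is a separate editorial defect that points to the same omission but is not its cause. This should be corrected because the cost is small and the exposure is in pregnancy. It does not affect the pain comparison.

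**What to change.** - At the existing 6-weeks-postpartum time point, complete a short birth record for all 60 randomised women: date and gestational age at birth, live birth or stillbirth, birth weight, neonatal unit admission, congenital anomaly.
- Take it from the woman or the obstetric record. For women who miss the visit or withdraw, use record review where consent allows.
- Add the row to Appendix I, and extend the pregnancy-outcome follow-up in e.iii to all women.
- Have it completed by staff without access to the randomisation code. Give counts by arm to the Data and Safety Monitoring Board, which section 3.5.2 says can access the code.
- Report the counts by arm with denominators, descriptively and without a test.
- Separately, complete b.iii if laboratory tests are planned, or delete it if none are. Only the sponsor can say which.

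The cost is one form, some record review, and releases for women who deliver elsewhere if the consent does not already cover them. There is no extra visit, blood draw or participant. The gain is limited: at 30 per arm the data can describe birth outcomes but cannot establish fetal safety.

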Patients will be approached in their second or third trimester regarding the study in the Obstetrics or Rehabilitation clinics if they have PGP. They will be given a flyer regarding the study. If interested in participating, they will either proceed to study visit 1 (baseline), if time permits, or set up a separate time for study visit 1 to take place. Patients will be consented and evaluated for eligibility at this baseline visit. Eligible patient will be randomized to either the control or intervention groups at study visit 1. They will receive the injected medication at study visit 1. This study will require study visits total, study visit 1 will be at the time of randomization,

study visit 2 will be 4 weeks after injection, study Visit 3 will be at 8 weeks after start of intervention/after injection. and study visit 4 will be 6 weeks post-delivery. There will be one follow-up phone call between visit 1 and 2 on day 7 following intervention to inquire about any medication side effects or adverse events. Study duration is 8 weeks per patient, with an expected two year total recruitment and data collection time period. At study visit 1, patients will be randomized to receive the intervention medication or active comparator and undergo a physical examination of the external musculoskeletal pelvis and will complete the NRS for 'worst pain' and 'mean pain' during the latest 48 hours, a pain diagram, a personal health information questionnaire regarding their pregnancy, past medical history, activity level and restrictions. Disability as measured by the Pelvic Girdle Questionnaire (PGQ) and Oswestry Disability Index (ODI), Health-Related Quality of Life (HRQL) measured by the Wellbeing NRS and work ability will be measured with one question from Workability Index i.e. "Current work ability compared with the lifetime best".

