3.3 Intervention

Experimental intervention: At the posterior sacroiliac joint ligament just inferior to the posterior superior iliac spine, 40mg of methylprednisolone acetate (1cc) combined with 1cc of 1% Lidocaine will be injected using a 1.5 inch 25 gauge needle. The medication will be injected unilaterally if pain is single sided or bilaterally for a total of 4cc of medication if the pain is in both

sacroiliac joint regions. The subject will subsequently receive once weekly physical therapy for 4 weeks.

Control intervention: At the posterior sacroiliac joint ligament just inferior to the posterior superior iliac spine, 2cc of saline with 1cc of 1% Lidocaine will be injected using a 1.5 inch 25 gauge needle. The medication will be injected unilaterally if pain is single sided or bilaterally for a total of 4cc of placebo saline if the pain is in both sacroiliac joint regions.

The subject will subsequently receive once weekly physical therapy for 4 weeks

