3.5.3 Intervention administration

The injection intervention will be administered at study visit 1 following successful recruitment and consent. Since physical therapy is considered standard of care treatment in the management of pregnancy related PGP, all participants will need to have failed PT.

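### The investigator-withdrawal rule names only pregnancy and fetal follow-up, so it can lead to outcome-related loss of the 4-week pain score and leaves new maternal events uncovered

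*Combined protocol and SAP*

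**What the plan says.** The Safety Monitoring Plan, part e (stopping rules), item iii, states: "The investigator may decide to stop a subject's participation in this trial at any time". The examples follow: "This may happen, for example, if the participant fails to comply with the protocol activities or experiences an adverse event". No threshold of severity, seriousness or relatedness is attached. After such a stop the team will, with the woman's consent, "continue to follow the participant off study drug for pregnancy outcome and fetal adverse events". Pain, disability and maternal adverse events are not named.

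Three other places determine how far this reaches:

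- Part a.i of the same plan: "An adverse event is defined as any symptom or medical problem experienced by the participant following consent to participate".
- Section 3.5.5 lists the adverse events to be recorded, among them "significantly worse pain at the 7 day post-injection phone check".
- Section 3.3, for both arms: "The subject will subsequently receive once weekly physical therapy for 4 weeks". Those sessions are protocol activities with which a woman may fail to comply.

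On timing of the study drug, Section 3.5.3 says: "The injection intervention will be administered at study visit 1". Section 3 says the same. Appendix I, however, marks Intervention at Day 7 as well as at Day 0.

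**The concern.** The rule is worded for a drug that continues over time. On the body text's account the drug is given at visit 1, so ending participation afterwards withdraws no injected drug. It ends assessments and possibly the remaining physical therapy.

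One recorded adverse event, worse pain at Day 7, is also an early reading of the primary outcome, taken before the 4-week NRS on which Appendix II bases the sample size. If women leave because of early pain or side effects, and these differ by arm, the 4-week comparison is made among women selected after randomization. The same rule leaves new infections, falls or non-obstetric admissions after removal without stated follow-up, in a trial of a steroid in pregnancy.

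**Working it through.** **1. The plan's own figure.** Inputs from Appendix II: difference 2 points; SD 25 mm, read as 2.5 NRS points; two-sided alpha 0.05; power 80%. The protocol's formula gives n = (3.96 × 2.5 / 2)² = 24.5, so 25 per group. This matches the stated 25, and the rest of the sensitivity table also reproduces.

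**2. Is power the problem?** Enrolment is 30 per group, so 5/30 = 16.7% can be lost before falling to 25. By normal approximation, power is 83.6% at 27 per group and 80.7% at 25. Power is largely protected; the issue is which women are lost.

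**3. Size of a selective loss (illustration).** Assumptions not in the documents: the women removed are the fraction p with the worst early pain; all are in one arm of 30; early and 4-week pain are normal with correlation r. The fall in that arm's 4-week mean is

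shift = r × 2.5 × φ(z) / (1 − p), with z the upper-p normal cut-off.

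- 3 of 30 (p = 0.10): z = 1.28, φ(z) = 0.1755, so 2.5 × 0.1755 / 0.90 = 0.49. For r = 0.5, 0.7, 1.0 the shift is 0.24, 0.34, 0.49.
- 5 of 30 (p = 0.167): z = 0.967, φ(z) = 0.250, so 2.5 × 0.250 / 0.833 = 0.75. For r = 0.5, 0.7, 1.0 the shift is 0.37, 0.52, 0.75.

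Relative to the 2-point target this is 0.24/2 = 12% up to 0.75/2 = about 37%.

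**4. Cross-check with a simpler model.** If the k women removed have 4-week scores g points worse than the rest of their arm, the arm mean falls by (k/30) × g. With g from 2 to 4, k = 3 gives 0.20 to 0.40 and k = 5 gives 0.33 to 0.67, which is a similar range.

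**5. Removals in both arms.** With 3 removed from control and 1 from steroid, the step 3 formula gives a net shift of about 0.15 (r = 0.5) or 0.21 (r = 0.7), instead of 0.24 or 0.34.

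**6. Direction.** A lower NRS is better. Removing worst-pain women from the control arm lowers its mean and shrinks an apparent steroid benefit; removing them from the steroid arm inflates it.

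**7. Does another section retain the data?** Section 3.8 names no analysis set and no missing-data method, and does not mention collection after a stop. The allowance in Section 3.7 is for loss to follow-up and premature delivery; investigator removal is not mentioned. No section says that a removed woman continues the outcome visits.

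**The case against.** The strongest reply is that e.iii is permissive. The investigator may stop a subject; nothing obliges removal after an ordinary adverse event. Section 3.5.5 asks that worse pain be recorded, and Section 3.5.4 invites women to report worsening pain in week 1 and then describes their return at 4 weeks. This stands: a reader might infer that women with worse Day 7 pain will be removed, or that scores already collected will be discarded, and the documents say neither. What they leave open is that such removal is allowed and that nothing keeps later scores.

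A reader might also infer that all maternal safety follow-up ends. That goes too far. Part a.iii requires changes in an ongoing adverse event to be recorded, Section 4 sends women with an adverse reaction to maternal-fetal medicine, and pregnancy outcome may capture obstetric maternal events. The gap is new non-obstetric maternal events after removal.

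Third, Section 3 blinds the injecting investigator and the participant. This limits deliberate selection by arm, and with no true effect pain-based removals have little reason to differ between arms. It does not prevent unequal removal if pain or steroid side effects do differ.

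Fourth, the figures in the illustration are near the upper end. Appendix I schedules no questionnaire at Day 7, only a telephone call. The listed event is a worsening, not the highest level, so cutting off the top tail probably overstates selection. The 37% figure needs perfect correlation, 5 of 30 removed and none in the other arm. All of this stands, and is why the figures are illustrations and not estimates.

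Finally, it is not settled by the documents that the drug is given only once: the Day 7 mark in Appendix I conflicts with the body text. The point does not depend on how that is resolved.

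**Conclusion.** The concern holds in a limited form. As written, e.iii can lead to outcome-related loss of the 4-week NRS, and of ODI and PGQ, and it leaves new non-obstetric maternal events after removal uncovered. This is more than missing detail, because the rule states what is kept after removal and that list omits the primary outcome.

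The size cannot be estimated from the documents, which give no expected removal rate. Under one-arm, worst-pain removal of 3 to 5 of 30 with SD 2.5 and correlation 0.5 to 1.0, the arm mean moves by about 0.24 to 0.75 points; with removals in both arms, less. The documents do not support saying that the rule will bias the trial, or that any bias would favour the steroid. A cheap improvement.

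**What to change.** Keep the investigator's discretion over treatment and add to e.iii:

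> Stopping study treatment or physical therapy does not end data collection. With the participant's consent, the scheduled Day 7 call and the 4-week, 8-week and 6-week-postpartum assessments (NRS, ODI, PGQ, examination, maternal and fetal adverse events) continue, and these data are analysed in the randomized group.

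Section 3.8 should carry a matching sentence on the analysis set. The off-study-drug phrase in e.iii and the Day 7 Intervention mark in Appendix I must be reconciled with the injection at visit 1 in Sections 3 and 3.5.3; this review takes no view on which is right.

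Cost: a short protocol amendment and matching consent wording, with no visits beyond those already scheduled. The small downside is that a few women are contacted who would otherwise have been released.
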